Next, participants will be asked to relax and keep their eyes opened and fixed on a cross-hair for six-minutes while resting state data are collected. Following this, participants will be exposed to alcohol, trauma and neutral cues. We will use a block design consisting of two 6-minute runs. During the alcohol cue run, participants will hear an audio recording describing in detail the last time they consumed alcohol. The alcohol cue run will be divided into two, 3-minute blocks of alcohol and neutral cues. During the trauma cue run, participants will hear an audio recording describing in detail their traumatic event. The trauma cue run will be also divided into two, 3-minute blocks of trauma and neutral cues. During the neutral cue run, participants will hear an audio recording describing something neutral, such as their typical morning routine. To minimize potential carry-over effects, the runs will be counterbalanced so that half of the subjects in the placebo group and half of the subjects in the NAC group are exposed to the alcohol cue first and the remaining participants in each group are exposed to the trauma cue first. T2*-weighted gradient-echo planar images (EPI) will be acquired with the following parameters: TR = 2000 ms, TE = 27 ms, flip angle = 76°, matrix 64 x 64, field of view = 23 cm, slice thickness = 3.7 mm with no gap, with 36 slices to cover the entire brain.

Subject Compensation. Subjects will receive \$50 for the baseline visit (plus \$25 bonus for showing up on schedule), \$25 for the medication initiation (randomization) visit, \$40 for completing each of the subsequent weekly visits during the treatment phase, and \$100 for the 3-month, \$100 for the 6-month, and \$100 for the 12-month post-treatment follow-up visits. Patients will also receive a \$25 bonus after completing the WK 6 and a \$60 bonus for completing WK 12 visit. Participants may also be eligible to participate in the optional MRI portion of the study. The participant may receive \$25 for script development, \$75 for the first neuroimaging visit and \$125 for the second neuroimaging visit. Compensation is available in the form of cash or check. Thus, the total amount subjects may receive for study participation is \$1190

STATISTICAL ANALYSES

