For hypotheses 3A and 3B, the following preprocessing and analytical parameters will be used. Preprocessing: Post-acquisition preprocessing and statistical analysis of imaging data will be performed using FEAT (FMRI Expert Analysis Tool) Version 5.98, part of FSL (FMRIB's Software Library). Data will be preprocessed using scripting tools from FEAT. Non-brain signal will be removed using FSL's BET brain extraction. Scans will be corrected for motion using FSL's linear registration and scans will be spatially smoothed using a Gaussian kernel of 8 mm FWHM. Participants with head motion ≥ 0.2 mm will be excluded from the analyses¹²⁷. Motion artifacts will be identified and scrubbed from each subject's data. Scans will be spatially co-registered with a standardized anatomical template (Montreal Neurological Institute) using a 12 parameter affine transformation. Analysis: Functional connectivity will be measured using a psychophysiologic interaction seed-based approach¹²⁹⁻¹³⁰. PPI analysis is used to assess the functional coupling between different brain regions. The PPI is defined as the change in connectivity of one area (i.e., the seed region) to another in relation to the experimental context (e.g., alcohol vs. neutral cues). PPI analyses for resting state, trauma and alcohol cues will be performed separately. Customized sq. wave forms representing the trauma run (1=trauma block and -1=neutral block) and the alcohol cue run (1=alcohol block and -1=neutral block) the duration of each block will be convolved with a double-gamma hemodynamic response function. A mask of the seed region will be made using a 12-mm diameter sphere located in the center of the AMY using the MNI coordinates (x, y, z = ± 22 , 0, -22). The transformation parameters described above will also be applied to the mask. For each subject, the mean corrected and high pass filtered time series of the BOLD signal in the AMY will be extracted and used in a single subject whole brain PPI analysis. The PPI model will include the task vector, time series of the BOLD signal in the AMY, a term representing the positive task x seed interaction, and a term representing the negative task x seed interaction. The first level analysis will generate contrast images of the parameter estimates for each of the four regressors. Voxels will be thresholded at $Z > 2.3$ using a corrected cluster threshold of $p = 0.05$. The contrast images of the parameter estimates of the positive and negative task x seed interactions will be combined for group-level t-tests to identify regions that exhibited altered connectivity with the AMY during the trauma and alcohol cues as compared to neutral cues. All group-level results will be thresholded at $Z > 2.3$ using a corrected cluster threshold of $p = 0.05$. Separate linear regression tests will be used to test for associations between PFC-AMY connectivity at baseline and improvement in AUD and PTSD symptoms during treatment. Changes in total standard drinks will be regressed against the parameter estimate obtained from the center voxel from each cluster that exhibited a significant task x seed interaction with the AMY at rest and in response to the alcohol cues (Hypothesis 3A). Changes in CAPS-5 total scores will be regressed against the parameter estimate obtained from the center voxel from each cluster that exhibited a significant task x seed interaction with the AMY at rest and in response to the trauma cue (Hypothesis 3B). Further exploratory analyses will examine change in PFC-AMY connectivity from pre- to post-treatment and associations with alcohol and PTSD outcomes, both within and between medication groups.

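### Cue-run order is balanced by design but absent from the cue-based models for Hypotheses 3A and 3B; adding it as a covariate is a minor, nearly free gain in precision

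*Combined protocol and SAP*

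**What the plan says.** The Neuroimaging Component describes an alcohol run and a trauma run, each with one cue block and one neutral block. It gives the reason for balancing them: "To minimize potential carry-over effects, the runs will be counterbalanced". The split is made within arm: "half of the subjects in the placebo group and half of the subjects in the NAC group are exposed to the alcohol cue first". Everyone else starts with the trauma cue. Resting data come earlier in the session: "resting state data are collected. Following this, participants will be exposed to alcohol, trauma and neutral cues".

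The analysis text for Hypotheses 3A and 3B (Statistical Analyses, Hypotheses) has three stages:

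- **First level.** "The PPI model will include the task vector, time series of the BOLD signal in the AMY", plus positive and negative task-by-seed interaction terms.
- **Group level.** The interaction contrast images "will be combined for group-level t-tests to identify regions that exhibited altered connectivity with the AMY during the trauma and alcohol cues", compared with neutral cues.
- **Prognosis.** "Separate linear regression tests will be used to test for associations between PFC-AMY connectivity at baseline and improvement in AUD and PTSD symptoms". The predictor is the "parameter estimate obtained from the center voxel from each cluster that exhibited a significant task x seed interaction".

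Run order appears at none of these stages. Two other covariate statements might have supplied it, and neither does. The rule under General covers baseline characteristics associated with the primary outcomes. The list under Exploratory Hypothesis 4 (age, smoking status, tissue composition) belongs to the glutamate model.

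**The concern.** Counterbalancing spreads carry-over evenly across participants, so it does not tilt the average map or favour an arm. It does not make the two order groups alike. Hypotheses 3A and 3B concern individual differences, with each person's connectivity estimate as the predictor. For about half the sample the alcohol-run estimate is taken after that person's trauma script. For the other half the trauma-run estimate follows the alcohol script.

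If order shifts cue-versus-neutral connectivity on average, the shift acts as error in the predictor and pulls the connectivity-outcome association towards zero. It also adds to the residual variance of the group maps. Because only clusters significant in those maps go forward to the regressions, the same noise can act at both stages. At stake is some precision for the cue-based half of Aim 3.

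**Working it through.** **The plan's nearest figure.** No figure in the documents depends on run order. The closest is the prognostic calculation under Power and Sample Size: d = 1.0, two-sided 5%, 80% power, N = 34. A two-sample t-test needs 16.7 per group, so 17 per group and 34 in total, with power 0.807. The figure reproduces.

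**Inputs from the documents**
- Order split 50:50 within arm (Neuroimaging Component).
- Imaging sample 140 of 200, and about 25% attrition (Power and Sample Size).
- Prognostic effect d = 1.0 (Power and Sample Size).

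**Assumptions, because the documents give no value**
- D, the mean difference between order groups in cue-versus-neutral connectivity, in within-group SD: 0.2, 0.5, 0.8 and 1.0.
- A true connectivity-outcome correlation of 0.30. As an alternative, the plan's d = 1.0 converted for equal groups: r = 1/√(1² + 4) = 0.447.
- The trial's attrition applies to the imaging sample: 140 × 0.75 = 105.
- Order is unrelated to clinical outcome.

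**Formulas**
- A 50:50 factor that shifts the predictor by D adds variance D²/4.
- The correlation is multiplied by 1/√(1 + D²/4).
- The effective size of a group map of 140 is 140/(1 + D²/4).
- Power by Fisher's z: Φ(atanh(r)·√(n − 3) − 1.96).

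**Example, D = 0.5, r = 0.30, n = 105.** The multiplier is 1/√1.0625 = 0.970, so r becomes 0.291. Then atanh(0.291) × √102 − 1.96 = 1.07, and power is 85.7%. With no shift, atanh(0.30) × √102 − 1.96 = 1.17, and power is 87.8%.

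| D (SD) | Multiplier on r | Added variance | Effective n of 140 | Power, r = 0.30, order omitted | Power, r = 0.447, order omitted |
|---|---|---|---|---|---|
| 0 | 1.000 | 0% | 140 | 87.8% | 99.8% |
| 0.2 | 0.995 | 1% | 139 | 87.5% | 99.8% |
| 0.5 | 0.970 | 6% | 132 | 85.7% | 99.7% |
| 0.8 | 0.928 | 16% | 121 | 82.4% | 99.4% |
| 1.0 | 0.894 | 25% | 112 | 79.3% | 99.0% |

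**With order in the model.** The shift is removed at the cost of one degree of freedom. Replacing n = 105 by 104 in the formula gives 87.5% at r = 0.30 whatever D is, a cost of about 0.3 points when there is no order effect.

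**Check by simulation** (20,000 replicates, n = 105, r = 0.30, D = 0, 0.5, 0.8, 1.0):
- Order omitted: 88.1%, 85.9%, 82.5%, 79.0%.
- Order included: 87.8%, 87.7%, 87.7%, 87.4%.

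**The case against.** The case for leaving the plan alone is substantial, and most of it stands.

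- **Carry-over is only potential.** The protocol gives no size, and at 0.2 SD the loss is negligible.
- **The contrast already removes part of it.** Each run has its own neutral block, and the task vector codes cue against neutral within the run. Carry-over that shifts both blocks equally cancels. Carry-over that fades during the second run need not cancel, so cancellation cannot be assumed in full. A shift of 0.5 to 1.0 SD in a within-run difference is nevertheless a strong assumption.
- **Half of each hypothesis is untouched.** Both 3A and 3B also use resting connectivity, which is recorded before any cue in that session.
- **On the plan's own effect size the omission barely matters.** The largest assumed shift takes power from 99.8% to 99.0%. That effect may be optimistic, but it is the plan's figure.
- **The remedy is partial.** An order term removes the difference between order-group means. Carry-over that varies from person to person stays in the predictor.

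A reader might infer that the missing term biases the maps or confounds NAC with placebo. The documents do not support this, because order is split evenly within each arm. A reader might also infer that the regressions rule out covariates. The text calls them separate, which is silence on covariates and not exclusion.

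What survives is narrow: order is a known, balanced design factor, no cue-based model names it, and including it costs almost nothing.

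**Conclusion.** The omission is real and minor. It concerns precision in the cue-based models for Hypotheses 3A and 3B, not validity.

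The size is conditional on an order effect that the documents do not quantify. At n = 105 and an assumed r of 0.30, the loss is under 1 point of power at 0.2 SD, about 2 at 0.5, about 5 at 0.8 and about 9 at 1.0. With r near 0.45, from the plan's d = 1.0, it is under 1 point throughout.

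It would be tempting to conclude that carry-over is degrading Aim 3, or that the equivalent of 28 of 140 participants is lost (140 − 112). That figure belongs to the 1.0 SD case alone, and nothing in the documents shows an order effect of that size, or any order effect.

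The argument for acting rests on the trade: about 0.3 points given up if there is no effect, and nearly all of the loss recovered if there is an average one.

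**What to change.** In the analysis text for Hypotheses 3A and 3B, prespecify run order (alcohol first or trauma first) as a mean-centred between-subject covariate in:

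1. the group-level connectivity models for the alcohol and trauma runs;
2. the regressions of change in drinks and change in CAPS-5 on cue-based connectivity.

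Centring keeps the group-map intercept as the average over the two orders. The resting-state models need no order term.

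The cost is one sentence and one degree of freedom per model. Order is assigned by design, so no new data are needed provided that each participant's order is kept in the analysis file.

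Separately and optionally, the protocol could state whether a participant keeps the same order at the second scan. It does not say, and the point bears only on the exploratory pre-to-post connectivity analyses.

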PROTOCOL TITLE: A Randomized Controlled Trial of N-Acetylcysteine for Alcohol Use Disorder and Comorbid PTSD

NCT02966873

November 9, 2019

PROTOCOL TITLE: A Randomized Controlled Trial of N-Acetylcysteine for Alcohol Use Disorder and Comorbid PTSD

The primary objective of the proposed Phase II study is to evaluate the effects of NAC in reducing (1) AUD severity and (2) PTSD symptomatology among individuals (N=200) with current AUD and PTSD. We will also use functional magnetic resonance imaging (fMRI) and proton magnetic resonance spectroscopy (MRS) to investigate the neural circuitry and neurochemistry underlying comorbid AUD/PTSD and prognostic indicators of positive treatment response. Secondary objectives are to evaluate the effects of NAC on impairment in associated areas of functioning (e.g., depression, anxiety, sleep, risky behaviors). In order to accomplish this we will (1) employ an intent-to-treat, double-blind, placebo-controlled randomized controlled trial that will consist of 12 weeks of treatment with NAC (2400 mg per day) or placebo medication; (2) examine standardized, repeated dependent measures of clinical outcomes at baseline, week 6, week 12, and 3-, 6-, and 12-month follow-up; and (3) employ advanced neuroimaging methodologies, a laboratory cue paradigm, and collect biologic measures of alcohol consumption. The following specific aims are proposed:

Specific Aim 1: To determine the efficacy of N-acetylcysteine (NAC), as compared to placebo, in reducing alcohol use severity.

Specific Aim 2: To determine the efficacy of N-acetylcysteine (NAC), as compared to placebo, in reducing PTSD symptomatology.

Specific Aim 3: To use multimodal neuroimaging techniques to investigate the pathophysiology underlying AUD and comorbid PTSD, and prognostic indicators of treatment outcome.

Human Subjects Involvement and Characteristics: A total of 200 adults between the ages of 18 and 70 will be recruited over a 5-year period. The inclusion/exclusion criteria are as follows:

Inclusion Criteria:

1. Male or female; any race or ethnicity; age 18 to 70 years old.
2. Subjects must be able to comprehend English.
3. Meet DSM-5 criteria for current alcohol use disorder (AUD).

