Primary Outcome Measures. The primary outcome measures are described in this section. Information regarding additional measures can be found in Table 1. The primary clinical outcomes include: (1) alcohol use severity (TLFB for alcohol consumption), and (2) PTSD symptom severity (CAPS-5 for clinician-rated and PCL-5 for self-reported symptoms). The TLFB obtains retrospective self-report of alcohol use by using a calendar and memory prompts to stimulate recall¹¹². Quantity and frequency of use are obtained (e.g., total number of standard drink units, percent of days drinking, heavy drinking days as defined as 5 or more drinks for a man or 4 or more drinks for a woman) as well as abstinence (yes/no). The TLFB will assess consumption of alcohol as well as nicotine and other substances for 60 days prior to study entry, weekly during treatment, and at follow-up. The TLFB yields consistently high test-retest reliability and convergent validity with other self-reports and collateral reports¹¹³. The OCDS is a 14-item self-report measure of craving with high internal consistency and concurrent validity and good predictive validity of future drinking¹¹⁴⁻¹¹⁵. The CAPS for DSM-5 is a 30-item structured diagnostic interview and gold standard for assessing PTSD¹¹⁶. The CAPS assesses trauma history and has excellent psychometric properties and diagnostic efficiency¹¹⁷. The PCL for DSM-5 is a 20-item self-report measure that assesses PTSD severity and has excellent psychometric characteristics^{116,118}.

STUDY INTERVENTIONS AND PROCEDURES

Overview. Subjects will be randomized to NAC or placebo, and all subjects will receive cognitive-behavioral therapy (CBT) targeting AUD (12, weekly 60-minute sessions). Note that subjects will not receive any other CBT or treatments during the study. All services received (e.g., self-help groups, case management) will be carefully monitored and tracked at weekly visits.

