General. Baseline clinical and demographic characteristics will be collected and contrasts performed between treatment groups. Continuous and ordinal characteristics will be compared using a Wilcoxon Rank-Sum test statistic. Categorical characteristics will be compared using a Pearson Chi-Square test statistic. Baseline characteristics found to be significantly associated with primary outcome measures will be included as covariates in the analyses. All analyses will be performed on the intent-to-treat sample consisting of all randomized subjects. All analysis will be conducted using SAS v9.3 (SAS Institute, Cary, NC, USA).

Randomization. We will stratify by (1) AUD severity (TLFB) and (2) PTSD severity (CAP-5). Stratified random block randomization will be used to balance the randomization assignment with respect to these strata. The purpose of stratification is to distribute these potential prognostic factors equally across treatment groups.

Power and Sample Size. This study is powered to estimate the efficacy of NAC on the reduction in PTSD symptoms, alcohol use, and craving at the end of the treatment phase (final 3 weeks of treatment). This study builds on a recently completed pilot trial of NAC that assessed efficacy in reduction of PTSD symptomology and craving in a cohort of Veterans with PTSD and substance use disorders. In this promising pilot trial, we observed a clinically significant decrease in CAPS total scores following 8 weeks of treatment with NAC ($\Delta=26.8$) while the placebo response was attenuated ($\Delta=17.1$). Assuming a similar difference in treatment effects in a larger population, we will have 80% power with a type 1 error rate of 5% to detect this difference with 75 participants randomized to each of the two treatment arms (total

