Hypotheses. The hypotheses and statistical approaches for testing each hypothesis are listed below.

Hypothesis 1: NAC treatment will result in significantly greater reduction in AUD severity and craving, as compared to placebo. To test this hypothesis, a mixed effects modeling framework will be specified with the total number of standard drinks consumed and the OCDS total score as the primary outcomes. A Poisson distribution will be assumed with a logarithm link function to assess the effects of NAC treatment and the baseline number of total standard drinks (past 60 days) prior to treatment entry. Over-dispersion due to a wider than expected distribution in discrete count models (from heterogeneity) can have a significant impact on parameter inference, thus when detected, a negative binomial (NB) distribution will be specified. Further, data collected in substance abuse studies often contain a preponderance of zeros, and these zeros in the distribution can be considered sampling zeros in the Poisson process¹²⁵. If this excess is present in the distribution, two-part Hurdle models (Poisson and NB) will be explored¹²⁶⁻¹²⁷. The hurdle part of the model will allow us to estimate the probability of abstinence during the study period (as an odds ratio) while the Poisson/NB portion will allow for the assessment of the risk of an increase in using days beyond zero during the study period (as a risk ratio). Model fit of the Poisson (Hurdle Poisson) model will be compared to the Negative Binomial (Hurdle NB) model by practical examination of the deviance and Pearson chi-square values (Likelihood Ratio) with respect to their degrees of freedom. Baseline alcohol use and craving will be included in pertinent models as covariates. Additional alcohol use outcomes will be assessed: percentage of drinking days (DD) and the number of heavy drinking day (HDD). End of study abstinence will be assessed using logistic regression models. DD and HDD will be assessed using count models.

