Hypothesis 2: NAC treatment will result in significantly greater reduction in PTSD severity as compared to placebo. To test this hypothesis, generalized linear mixed effects regression models with a Gaussian distribution will be developed to assess group differences while adjusting for baseline CAPS-5 scores. Assumptions of residual normality and homoscedasticity will be checked using statistical test and graphical methods (Residual and Q-Q plots, and Shapiro-Wilk tests) and transformation will be done as necessary. Restricted maximum likelihood (REML) methods will be used to estimate the fixed effects and variance components.

Hypothesis 3A: Prefrontal cortex-amygdala connectivity at rest and in response to alcohol vs. neutral cues will predict reduction in alcohol use severity (total standard drinks).

Hypothesis 3B: Prefrontal cortex-amygdala connectivity at rest and in response to trauma vs. neutral cues will predict reduction in PTSD severity (CAPS-5).

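### Each clinical aim has two declared primary outcomes and no rule for combining them, and the Hypothesis 1 and 2 models do not name the end-of-treatment contrast for which power is stated

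*Combined protocol and SAP*

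**What the plan says.** The opening objective is to "evaluate the effects of NAC in reducing (1) AUD severity and (2) PTSD symptomatology among individuals", and Specific Aims 1 and 2 take these in turn. The Primary Outcome Measures section states: "The primary clinical outcomes include: (1) alcohol use severity (TLFB for alcohol consumption"), and as the second item "2) PTSD symptom severity (CAPS-5 for clinician-rated and PCL-5 for self-reported symptoms"). The same section describes OCDS but leaves it out of that numbered list.

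Power and Sample Size covers PTSD symptoms, alcohol use and craving "at the end of the treatment phase (final 3 weeks of treatment"). CAPS and craving are each powered at a 5% type 1 error rate. The statement for drinks gives no alpha.

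Hypothesis 1 specifies a mixed model "with the total number of standard drinks consumed and the OCDS total score as the primary outcomes". Other drinking measures rank lower: "Additional alcohol use outcomes will be assessed: percentage of drinking days (DD) and the number of heavy drinking day (HDD"). Hypothesis 2 specifies Gaussian mixed models adjusted for baseline CAPS-5 and mentions no other scale. Neither hypothesis gives a visit, a time term or a contrast. Clinical outcomes are collected at weeks 6 and 12 and at 3, 6 and 12 months after treatment, and TLFB is also collected weekly during treatment.

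**The concern.** With two primaries in an aim, the reader has to know whether one success is enough or both are needed. The first raises the false-positive rate of the aim's claim above 5%, and the second lowers its power. The plan gives no rule, so neither figure can be read from it.

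The time point has a similar gap. A repeated-measures model can give a week-12 effect, an average over treatment or an average through month 12. Power was stated for the end of treatment only. If the model does not name that contrast, the effect tested need not be the effect powered, and the choice could be made after the data are seen without departing from the text.

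**Working it through.** **1. The four outcomes side by side.**

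| Outcome | Primary Outcome Measures | Power and Sample Size | Hypotheses 1 and 2 |
|---|---|---|---|
| Total standard drinks | listed, through TLFB | risk ratio 0.75, at least 80% power, no alpha | primary |
| OCDS | described, not in the numbered list | change 3.0 v 1.3, over 95% power at 5% | primary |
| CAPS-5 | listed | CAPS change 26.8 v 17.1, 80% power at 5% | only PTSD scale named |
| PCL-5 | listed | none | not named |

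So Aim 1 has drinks and OCDS, and Aim 2 has CAPS-5 and PCL-5. The only error-rate correction in the Statistical Analyses is the cluster threshold for the imaging maps.

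**2. The plan's own figures.** The attrition step reproduces: 75 / (1 - 0.25) = 100 per arm. The 75 per arm cannot be checked, because no SD is given. Solving backwards (two-sided 5%, 80% power, difference 26.8 - 17.1 = 9.7): SD = 9.7 × √(75/2) / (1.960 + 0.842) = 21.2, or d = 0.46.

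**3. False-positive rate per aim if either outcome suffices.** Assume two-sided tests at 5% (sidedness is not stated for the clinical tests) and test statistics that are bivariate normal with correlation r. The rate is 1 - P(|Z1| < 1.96 and |Z2| < 1.96). At r = 0 it is 1 - 0.95² = 9.75%. The documents give no correlations, so a range is assumed:

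| r | 0.3 | 0.5 | 0.6 | 0.7 | 0.8 | 0.9 |
|---|---|---|---|---|---|---|
| rate | 9.5% | 9.1% | 8.7% | 8.4% | 7.8% | 7.0% |

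For drinks and OCDS, r = 0.3-0.7 gives 9.5-8.4%. For two scales of the same PTSD construct, r = 0.6-0.9 gives 8.7-7.0%.

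**4. Power per aim if both must succeed.** There is no inflation. At the stated lower bounds, Aim 1 power is 0.80 × 0.95 = 0.76 if the tests are independent. It rises with positive correlation but cannot exceed 0.80. For Aim 2 it cannot exceed the 80% for CAPS, and it cannot be computed because PCL-5 has no power statement.

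**5. Time point.** Power is tied to the final 3 weeks. Neither Hypothesis 1 nor Hypothesis 2 says which of the visits through month 12 enter the model or at which one the groups are compared. The exploratory glutamate model under Hypothesis 4 does name time as a factor.

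**6. What adjustment would cost.** Under Holm with two tests, an outcome succeeds if it passes at 2.5%, or if the other passes at 2.5% and it passes at 5%. An outcome with 80% power at 5% has Φ(2.802 - 2.241) = 0.712 at 2.5%. One with 90% has Φ(3.242 - 2.241) = 0.841, and one with 95% has Φ(3.605 - 2.241) = 0.914. With independent tests:

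- CAPS with drinks at 80%: 0.712 + 0.712 × (0.800 - 0.712) = 0.775. Simulation at r = 0.3 and 0.5 gives 0.768 and 0.765.
- CAPS with drinks at 90%: 0.712 + 0.841 × 0.088 = 0.786. Simulation at r = 0.3 and 0.5 gives 0.782 and 0.780.
- Within Aim 1, drinks with OCDS: 0.712 + 0.914 × 0.088 = 0.792.

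**The case against.** The strongest reply is that the plan is clearer than the concern suggests, and much of that reply stands.

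- **Main variables.** A reader might infer that the alcohol and PTSD endpoints are left open. They are not. The power statements use standard drinks and CAPS. Hypothesis 3A says connectivity "will predict reduction in alcohol use severity (total standard drinks"), and 3B says it "will predict reduction in PTSD severity (CAPS-5"). Drinking days and heavy drinking days are labelled additional.
- **OCDS.** A reader might infer that the sections conflict over OCDS. They do not: it is described under the primary heading, powered, and named as primary in Hypothesis 1. The numbered list is incomplete.
- **PCL-5.** Hypothesis 2 speaks of models, in the plural, for PTSD severity, which might be meant to cover PCL-5. That is possible, but only baseline CAPS-5 is named as a covariate.
- **Success rule.** Hypothesis 1 joins AUD severity and craving with a conjunction, which could mean that both are required. That reading removes the inflation for Aim 1. It is not stated as a decision rule, and it would lower power.
- **Both aims together.** A reader might count all tests across the trial: 14.3% for three independent tests or 18.5% for four. The documents do not support this as the size of the problem. The two aims are set out separately, four independent tests are implausible here, and error control across separate aims in a Phase II trial is a design choice.
- **Time window.** A reader might take the reference to the study period in Hypothesis 1 as a competing window. It describes only the parts of a hurdle model to be explored if zeros are in excess. The final 3 weeks is the one documented window, but the models do not take it up.

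What remains is the missing rule within each aim, the unstated role of PCL-5, and the missing contrast.

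**Conclusion.** The concern holds within each aim and should be fixed before unblinding. Two declared primaries per aim have no combining rule. If either suffices, the error is about 8.4-9.5% for Aim 1 and 7.0-8.7% for Aim 2. If both are needed, there is no inflation, and Aim 1 power is about 76-80% at the stated lower bounds. The plan states neither rule, so these are conditional figures and not the plan's actual error rate. They rest on two-sided 5% tests and assumed correlations.

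The time-point gap needs no assumption: the powered window does not appear in the Hypothesis 1 or 2 models. This is a defect of specification and does not show that the wrong visits would be analysed.

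**What to change.** Before unblinding:

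1. Use one primary list in Primary Outcome Measures, Power and Sample Size, and Hypotheses 1 and 2, with one main variable per aim: total standard drinks in the final 3 weeks of treatment, and CAPS-5 total at week 12. Make PCL-5 secondary. Make OCDS either secondary or a second Aim 1 test at an overall 5%, by Holm or in fixed order after drinks.
2. Name the visits in each mixed model, include treatment-by-visit terms, and make the end-of-treatment contrast the primary test.
3. State that the two aims are separate claims, each at 5%, and give the alpha for the drinks power statement. Control across both aims is optional.

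The cost is wording and a little analysis work, with no new data. With separate aims, CAPS power stays at 80%. Keeping OCDS in fixed order after drinks leaves drinks at its stated power; Holm lowers drinks from 80% to about 79%. If the sponsor prefers Holm across drinks and CAPS-5, CAPS power is about 76-77% with drinks power at 80%, and about 78-79% with drinks at 90%. Both are shown because the stated drinks power is a lower bound.
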